11.2. Adverse Event of Special Interest of Dizziness

The adverse event of special interest of dizziness will also be recorded in detail, and narratives will be generated for this AE of special interest with Grade 2 or above. The additional information that will be collected for AEs of dizziness are noted in Table. The AEs of dizziness will be characterized in a summary table, by treatment cohorts and combined lenabasum cohorts, cumulatively through Visit 8 and during the 28-day safety follow-up period. The characteristics will include age, gender, race, past history of dizziness, dizziness AEs that lead to permanent study product or study discontinuation, maximum severity, strongest relationship to study product, day or onset, duration, number of subjects with recurrent AEs of dizziness, and occurrence period while receiving active treatment drug (all, \leq Day 30, $>$ Day 30 to \leq Day 90, \geq Day 90 through Visit 8) and during the safety follow-up period).

Table 2 Adverse events of special interest and information to be collected

Adverse event of special interest	Additional information to be collected
Dizziness/light-headedness	
• If intermittent or a single event, average duration of episode in minutes• Temporal relationship to dose (when was the last dose of study drug prior to start of AE)• Was it associated with vertigo• Was it positional (orthostatic)• Any other associated symptoms (if yes please report them separately in AE)

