4.1.7. Duration of Study

The intended duration of active dosing is 28 weeks (through Visit 8).

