4.2. Study Efficacy Endpoints

4.2.1. Primary Efficacy Endpoint

The primary efficacy endpoint is the event rate of new PEx per subject per 28 weeks using the primary definition of new PEx comparing the lenabasum 20 mg BID and placebo cohorts. The event rate is based on the occurrence of new PEx, and the occurrence will be assessed during the treatment phase. It is defined as follows:

The primary endpoint will be calculated by the following for each treatment cohort:

Event rate of PEx (per subject-28 Weeks) for a treatment group is calculated as follows:

Total number of PEx using primary definition during the treatment period / [sum of subject treatment exposure durations in the treatment group (days) / 196]

[figure not shown]
Event rate of PEx (per subject) for a treatment group (without adjustment of treatment exposure) is calculated as follows:

Total number of PEx using primary definition during the treatment period / number of subjects in the treatment group

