6. GENERAL STATISTICAL CONSIDERATIONS

6.1. Reporting Conventions

All data analysis will be performed by Statistics & Data Corporation after the study is completed and the database has been locked. The following reporting conventions will be used:

- Outputs will be provided in rich text format for tables and portable document format for tables, listings, and figures using landscape orientation.
- Data from all study centers will be combined for analysis.

- All study data will be listed by subject, treatment, and visit (as applicable) based on all randomized subjects unless otherwise specified. Additional data listings will be provided as described in the sections for the data analyses.
- Summaries for continuous and ordinal variables will include: the number of observations (n) of observations, arithmetic mean, standard deviation (SD), median, minimum (min), maximum (max). Unless specified in the actual table shells, the mean, median, first quartile, second quartile, third quartile, (interquartile range), the upper and lower limits of the confidence interval (CI) will be displayed to one more decimal place than the original data (derived analysis data). Standard deviation and standard error values will be displayed to two more decimal places than the original data. Minima and maxima will be displayed to the same number of decimal places as the original data. Summaries for discrete variables will include frequency counts and percentages. All percentages will be rounded to one decimal place (i.e., XX.X%).
- The number and percentage of responses will be presented in the form XX (XX.X%), where the percentage is in parentheses. The denominator of all percentages will be number of subjects in the analysis population, unless otherwise stated. When count data are presented, the percent will be suppressed when the count is zero in order to draw attention to the non-zero counts. A row denoted “Missing” will be included in count tabulations where necessary to account for dropouts and missing values. Non-zero percentages will be rounded to one decimal place, except 100% will be displayed without any decimal places.
- The day of the first dose of study product will be defined as Day 1, which is the day of Visit 1. All study days before Day 1 will be calculated as (assessment date – first dose date of study product). The study day on or post Day 1 will be calculated as (assessment date - first dose date of study product + 1).

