8.2. Study Treatments

8.2.1. Extent of Exposure

Treatment exposure duration will be defined as the number of days that the subject was exposed to study treatment as calculated using the formula:

$$\text{Exposure duration (days)} = \text{date of last dose} - \text{date of first dose} + 1.$$

Last dose date will be imputed using last contact date during active treatment for the subjects lost to follow up and as the date of the last visit seen, excluding safety follow-up visit, for subjects missing last dose date.

The duration of exposure will be summarized for treatment cohorts and combined lenabasum cohort. All summaries will be based on the safety population. Summary statistics will be presented for treatment exposure.

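### The on-treatment dizziness onset periods overlap at Day 90, so an onset on that day falls in two of them

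*SAP*

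**What the plan says.** SAP Section 11.2 plans a summary table of dizziness by treatment cohort and for the combined lenabasum cohorts. One of its rows is the "occurrence period while receiving active treatment drug". The on-treatment categories are all onsets, onsets up to and including Day 30, onsets after Day 30 up to and including Day 90, and onsets from Day 90 itself to Visit 8. The last two are printed as "Day 30 to \leq Day 90, \geq Day 90 through Visit 8". The safety follow-up is a further category. The same table also reports "day or onset, duration, number of subjects with recurrent AEs of dizziness", where the first item is evidently meant to be day of onset.

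Three other provisions bear on the point:

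- Section 6.1 fixes the day count: "The day of the first dose of study product will be defined as Day 1, which is the day of Visit 1".
- Section 6.1 also sets the default for percentages: "The denominator of all percentages will be number of subjects in the analysis population, unless otherwise stated". Section 11.2 states nothing different for the onset periods.
- Section 8.2.1 deals with time on product for the whole treatment period only: "The duration of exposure will be summarized for treatment cohorts and combined lenabasum cohort". It does not divide exposure by onset period.

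**The concern.** A set of onset periods should place each event in exactly one category. The Day 30 boundary does so: the first period includes Day 30 and the second starts after it. The Day 90 boundary does not, because both neighbouring periods include that day. A programmer who follows the text must count a Day 90 onset twice, and one who does not must choose a period without guidance from the SAP. Under Section 2 the sponsor will not change the SAP once it is signed, apart from analyses that FDA requests, so the slip is best settled beforehand.

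A lesser matter is the denominator. Section 11.1 confines treatment-emergent events to the time from first to last dose, and Section 4.1.12 lets a subject stop product and remain in the study. Such a subject cannot contribute an on-treatment onset afterwards but still counts in the default denominator. Section 11.2 itself tabulates dizziness that leads to permanent discontinuation, so the event of interest can itself reduce the number at risk in later periods. The table as specified does not show by how much.

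**Working it through.** **Inputs from the SAP.** First dose is Day 1 (Section 6.1). Dosing lasts 28 weeks (Section 4.1.7), and 28 × 7 = 196 days, which agrees with the divisor in Section 4.2.1, "sum of subject treatment exposure durations in the treatment group (days) / 196". Planned cohort size is 166 for lenabasum 20 mg BID, with 415 subjects in total (Sections 4.1.5 and 4.1.9). Drop-out is about 15% (Section 4.1.5).

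**Step 1: count the days in each period, taking Visit 8 as Day 196.**

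| Period | As printed | Last period starting after Day 90 |
|---|---|---|
| First | Days 1–30: 30 | 30 |
| Second | Days 31–90: 60 | 60 |
| Third | Days 90–196: 107 | Days 91–196: 106 |
| Sum | 197 | 196 |

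The only day common to two periods is Day 90. If Visit 8 falls on Day 197, the sums are 198 as printed and 197 corrected, so the surplus is again one day.

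**Step 2: size of the double count.** If onsets are uniform over 196 days, the share falling on Day 90 is 1/196 = 0.51%. The SAP gives no expected incidence of dizziness, so I assume 5% to 20% of subjects, with at most one event each.

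- Expected Day 90 onsets, n × incidence / 196: for n = 166, 166 × 0.05 / 196 = 0.04 to 166 × 0.20 / 196 = 0.17; for n = 415, 0.11 to 0.42.
- Chance of at least one, 1 − (1 − incidence/196)^n: about 4% to 16% for n = 166, and about 10% to 35% for n = 415.

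**Step 3: how far the default denominator departs from the number on product.** Assume that the 15% drop-out also describes stopping product, at a constant hazard λ = −ln(0.85)/196. Mean days on product per subject between days a and b are (e^(−λa) − e^(−λb))/λ.

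| Period (corrected) | Length, days | Mean days on product | Average share on product |
|---|---|---|---|
| Days 1–30 | 30 | 29.6 | 0.99 |
| Days 31–90 | 60 | 57.1 | 0.95 |
| Days 91–196 | 106 | 94.2 | 0.89 |

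On this assumption about 11% (1 − 0.89) of the nominal subject-time in the last period is not time on product. It would be more if some subjects stop product and remain in the study, since drop-out does not count them.

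**The case against.** The strongest reply is that this is one wrong symbol in a descriptive table, and much of that stands. The double count needs an onset on exactly Day 90. The row for all onsets gives the total without duplication. Where subjects are counted, the periods need not sum to that total even with clean boundaries, because a subject with recurrent dizziness can appear in more than one. Day of onset is summarised in the same table, events of special interest are listed by subject (Section 11.1), and Section 11 plans no formal safety testing.

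It can also be said that periods of unequal length are a legitimate descriptive choice. That stands too. The columns are treatment cohorts, and within one period the window length is the same for each and cancels. Only different rates of stopping product between cohorts would disturb that comparison. The SAP does not say that such a difference exists; the table simply could not reveal it.

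A reader might infer more: that the onset pattern will be misread, or that the long last period dilutes an early effect. The SAP supports neither. Under constant risk the corrected periods would hold 30/196 = 15%, 60/196 = 31% and 106/196 = 54% of onsets, but those proportions can be seen from the row labels, and the length of the later periods does not alter the count for Days 1–30. Nor does the SAP state that the table is meant to test for an early, transient effect.

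**Conclusion.** The overlap is an error as written: Day 90 belongs to two periods, and followed literally the rule counts a Day 90 onset twice. Its expected size is small, about 0.5% of onsets if they are uniform, and most likely no affected event in a single 166-subject cohort at the assumed incidence of 5% to 20%. No efficacy result is touched. The case for correcting it is that the SAP should not contain a rule that cannot be programmed consistently, and that the correction is not open to dispute.

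The denominator point is a modest improvement to the table and not a second error. It rests on Sections 4.1.12, 6.1 and 11.1 read together. The 0.89 average share in the last period rests on the planned 15% drop-out at a constant hazard, applied to time on product.

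**What to change.** In Section 11.2, replace the ≥ sign before the second Day 90 with >, so that the last on-treatment period begins on Day 91 and runs through Visit 8. The periods then hold 30 + 60 + 106 = 196 days without overlap. The cost is one symbol.

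As an addition, show for each period and cohort either the number of subjects still on product at the start of the period or the subject-days on product within it. First- and last-dose dates already feed the exposure calculation in Section 8.2.1, so no new data are needed. Because that formula runs from first to last dose, the footnote should say that interruptions are not deducted. The cost is one extra row per period. If the SAP has already been signed, the boundary used can be recorded in the clinical study report, as Section 14 provides.

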11.3. Clinical Laboratory Tests

For serum chemistry and hematology, the results for each parameter in the International System of Units will be summarized by treatment and visit using continuous summaries. Change from baseline and shift tables will also be provided comparing post-baseline visits with baseline.

For urine dipstick tests, the results for each parameter will be summarized by treatment at each visit using number of subjects and percentages for each result category.

Serum and urine pregnancy test results will be provided in a data listing only.

11.4. Vital Signs

Vital signs will include systolic blood pressure, diastolic blood pressure, pulse rate, respiratory rate, body temperature, oxygen saturation, weight, and height as safety endpoints. BMI is an efficacy endpoint and the analysis of BMI is included as a tertiary efficacy outcome ([Sections 5.3.3](#) and [9.6.3](#)).

The actual values and change from baseline for every post-baseline visit in each parameter will be summarized by treatment and visit.

11.5. Physical Examination

Physical examination results will be presented in a listing only. A listing of medically significant abnormal physical examination results will also be provided.

11.6. Twelve-Lead Electrocardiogram

[figure not shown]
Electrocardiogram (ECG) parameters include heart rate, RR interval, QRS duration, PR interval, QT interval, QT interval correction by Fridericia's formula, and if needed by Bazett's formula. In addition, ECG evaluation of abnormality and interpretive statements will also be reported.

The actual values and change from baseline for every post-baseline visit/time point in each ECG parameter will be summarized by treatment and visit/time point.

Electrocardiogram evaluation of abnormality (normal versus abnormal) will be summarized by treatment and visit/time point using number and percentage of subjects in each result category.

11.7. Analyses of Safety Endpoints for Subjects at Sites in France Only

Safety endpoints derived from questionnaires answered by subjects at sites in France only ([Section 4.3.3](#)) will be provided in subject data listings and summarized descriptively by treatment cohort and the combined lenabasum cohort. The analyses will be based on the safety population in France and done at the visits at which the data are collected for the relevant endpoint.

13. CHANGES FROM PROTOCOL-STATED ANALYSES

- The randomization schedules were initially set up stratified by 1 or 2 versus 3 number of previous PEx requiring IV antibiotics in the previous year as per protocol version 1. Protocol version 3.1 states that the randomization is stratified by 1 versus 2 or 3 number of previous PEx requiring IV antibiotics in the previous year. However, the IWRS was not updated to reflect this change until after 185 subjects had been randomized. Therefore, the number of previous PEx is treated as a continuous variable in the model for the primary and secondary efficacy endpoints.
- The efficacy and safety analyses will generally be based on on-treatment, from start of treatment to end of the treatment period at Week 28. For subjects discontinuing the study early, the treatment period will end at time of discontinuation. The safety follow-up period will be summarized separately for the AEs.
- Additional analyses and methods for handling missing data due to COVID-19 have been incorporated as described in [Section 4.1.14](#), according to recommendations from the FDA COVID-19 related Guidance dated March 2020 and June 2020.
- Additional detail has been added to the SAP regarding the tertiary objectives to facilitate programming and analyses.
- Baseline CFTR-targeting medications use (Yes; No) was added to applicable statistical models.

14. CHANGES FROM STATISTICAL ANALYSIS PLAN

Changes from this statistical analysis plan will be described in the statistical analysis section of the CSR.

